Initial data characteristics will be compared between groups using chi-square for categorical variables and t-test or Wilcoxon rank sum test for continuous variables. Change in pain from baseline will be compared between two treatment groups using chi-square test for binary variable and t-test or equivalent non-parametric test for continuous variable, as appropriate. The significance level of the test will be targeted at $\alpha=0.05$ (one sided). Non-inferiority will be established, at the 0.05 significance level if the lower limit of equivalent two-sided 90% confidence interval for the difference in success rate is above non-inferiority margin. Multivariable linear regression analysis will be performed to examine the changes in pain score adjusting potential confounders such as type of pain (lumbar vs. other), prior duration with pain. Reports of side effects will also be investigated between two groups. As an exploratory analysis we will evaluate the time to onset of action between two topical drugs, where time to onset variable will be measured within 1 hour (as \leq 15 min, \leq 30 min, \leq 45 min or \leq 60 min) after the application of drugs at clinic. No adjustments will be made for the multiple endpoints testing. All analyses will be conducted using SAS version 9.4.

Analysis will be performed for the full datasets and by pain group (acute and chronic).

Power Calculation:

Preliminary data to base on power analysis

Meta-analysis from Massey et al (Cochrane Database Syst Rev.; (6) 2014) presented data from combined three studies comparing topical diclofenac versus placebo (Joussellin 2003; Predel 2004; Rowbotham 2003). A total of 319 participants were treated with topical diclofenac, and 307 with placebo. The success rate (i.e. patient reported pain relief at least 50%) was 52% (166/319, range 39% to 92%) for group treated with diclofenac and 25% (77/307, range 8% to 36%) for placebo group.

Assumptions behind power calculations:

There will be two equal-sized treatment arms, one containing diclofenac topical solution 1.5% treated patients and the other Bonipar treated patients. The arms will be compared for a difference in success rate (i.e. pain reduction at least 50% from baseline to follow-up at 1 weeks) with Z-test (one-sided at alpha=0.05) using PASS software. Two scenarios will be considered, as follows:

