1. The success rate will be 52% among diclofenac topical solution 1.5%vs. 62% true success rate among Bonipar group (with -10% non-inferiority margin)
2. The success rate will be 52% among diclofenac topical solution 1.5%vs. 67% true success rate among Bonipar group (with -10% non-inferiority margin)

Difference $D_0 = P_2 - P_1$ (non-inferiority margin)

$H_0: P_2 - P_1 \leq D_0$

$H_1: P_2 - P_1 = D_1 > D_0$

D_1 : True observed difference i.e. $P_1(H_1) - P_2$

Where P_1 & P_2 represent the proportion of success for Bonipar and diclofenac topical solution 1.5% group respectively.

Statistical power and required sample size for the aforementioned two scenarios are presented in the table.

| Power | Alpha | D_0 | D_1 | P_2 | $P_1(H_0)$ | $P_1(H_1)$ | N_1 | N_2 | Total N |
|-------|-------|-------|-------|-------|------------|------------|-------|-------|---------|
| 0.80 | 0.05 | -0.10 | 0.10 | 0.52 | 0.42 | 0.62 | 76 | 76 | 152 |
| 0.80 | 0.05 | -0.10 | 0.15 | 0.52 | 0.42 | 0.67 | 49 | 49 | 98 |

Pass software was used to determine sample size of the study. With a sample size of 152 (76 per group), we will be able to achieve 80% statistical power to detect a difference in success rate on pain reduction of 10% between Bonipar and diclofenac topical solution 1.5% groups with a non-inferiority margin of 10%. If we consider a 10% drop out rate, we will need to enroll 8 more patients per group a total of 168. This 10% drop out rate did not reflect the patient population. Consequently, we plan to consent 240 subjects in order to reach our target goal of 152 completed subjects.

Interim Analysis:

After approximately 50% of the study is completed (75 to 95 patients), we plan to carry a preliminary statistical analysis of the patients who have completed the study at that time.

We do NOT plan to analyze the primary data i.e. the pain scores of the two groups because that process could potentially interfere with the non-inferiority integrity of the final analysis of that data.

We are therefore proposing on the advice and approval of our Consultant Statisticians:

- 1) to analyze all the data as one group and not to differentiate between the group receiving the study drug and the group receiving Diclofenac.
- 2) to analyze the secondary data including adverse effects and dropout status from the study and to perform a comparative analysis between the two groups.

Data & Safety Monitoring

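### The D0, H0 and H1 lines subtract Bonipar from diclofenac, the reverse of the D1 line, the scenarios and the sample size table, and the decision rule names no direction

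*Combined protocol and SAP*

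**What the plan says.** All of this is in Data Analysis & Statistical Considerations of the combined protocol and SAP.

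- **Labels (Power Calculation):** "Where P_1 & P_2 represent the proportion of success for Bonipar and diclofenac topical solution 1.5% group respectively". So P1 is Bonipar and P2 is diclofenac.
- **Margin line:** "Difference $D_0 = P_2 - P_1$ (non-inferiority margin"). The next two lines keep that order: H0 is P2 − P1 ≤ D0, and H1 is P2 − P1 = D1 > D0.
- **D1 line, directly below:** "D_1 : True observed difference i.e. $P_1(H_1) - P_2", the opposite order.
- **Scenario 1:** "The success rate will be 52% among diclofenac topical solution 1.5%vs. 62% true success rate among Bonipar group (with -10% non-inferiority margin"). Scenario 2 is the same with Bonipar at 67%.
- **Table, row 1** (power, alpha, D0, D1, P2, P1(H0), P1(H1), N1, N2, total): "0.80 | 0.05 | -0.10 | 0.10 | 0.52 | 0.42 | 0.62 | 76 | 76 | 152". Row 2 has D1 = 0.15, P1(H1) = 0.67 and 49 per arm.
- **Decision rule (analysis text before the Power Calculation):** non-inferiority is established "if the lower limit of equivalent two-sided 90% confidence interval for the difference in success rate is above non-inferiority margin". Neither the order of subtraction nor the signed margin is given there.

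**The concern.** The H0/H1 pair is the only formal statement of the primary non-inferiority hypotheses, and its sign disagrees with the table that sizes the trial. Read as written with D0 = −0.10, it asks whether diclofenac is no more than 10 points worse than Bonipar. The stated objective is the reverse: to evaluate Bonipar against diclofenac.

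The decision rule does not settle the matter, because it speaks only of the difference in success rate. An analyst who programs from the hypothesis lines would reverse the test. The bottles are labelled only Drug A and Drug B, so blinded analysis code needs the order of subtraction fixed in advance. Settling the sign after the arms are known would invite the charge that it was chosen to suit the result.

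**Working it through.** **1. Can the lines all hold?** Inputs are the labels and table values above.

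- At the table's null, P1(H0) = 0.42 and P2 = 0.52. Then P1 − P2 = −0.10, which matches D0. But P2 − P1 = +0.10, which does not.
- H1 sets P2 − P1 = D1, and the next line sets D1 = P1 − P2. Both hold only if D1 = 0. The table gives D1 = +0.10 (0.62 − 0.52) and +0.15 (0.67 − 0.52).
- Exchanging the labels does not rescue the text. The table would then put Bonipar at 52% and diclofenac at 62% or 67%, against both scenarios.

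**2. Reproduce the plan's sample sizes as Bonipar minus diclofenac.** One-sided alpha 0.05 (z = 1.645), power 0.80 (z = 0.842), and distance from the margin d = P1(H1) − P2 + 0.10. With the null variance taken at P1(H0) = 0.42:

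n = [1.645·√(0.52·0.48 + 0.42·0.58) + 0.842·√(0.52·0.48 + P1(1 − P1))]² / d²

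- Scenario 1: P1 = 0.62, d = 0.20, n = 75.8, so 76 (stated 76).
- Scenario 2: P1 = 0.67, d = 0.25, n = 48.03, so 49 (stated 49).

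Unpooled variance gives 75 and 47; pooled variance gives 76 and 48. The continuity-corrected version gives about 85 and 55 and does not match.

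Exact enumeration of the two binomials, declaring non-inferiority when the 90% Wald lower limit exceeds −0.10, agrees with the table:

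| Bonipar rate | Per arm | Exact power |
|---|---|---|
| 62% | 76 | 80.0% |
| 62% | 75 | 79.7% |
| 67% | 49 | 81.0% |
| 67% | 48 | 79.9% |

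**3. Apply the written direction, P2 − P1 with D0 = −0.10.** The distance from the margin is P2 − P1 + 0.10.

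- Scenario 1: 0.52 − 0.62 + 0.10 = 0. The planning alternative lies on the null boundary.
- Scenario 2: 0.52 − 0.67 + 0.10 = −0.05. The planning alternative lies inside the null.

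No sample size gives 80% power in either case, so the table cannot have come from the written hypotheses.

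**4. Size of the reversal.** Exact probability of declaring non-inferiority, 76 per arm, diclofenac 52%:

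| True Bonipar rate | Bonipar minus diclofenac | Diclofenac minus Bonipar (as written) |
|---|---|---|
| 42% | 5.0% | 79.8% |
| 62% | 80.0% | 4.9% |

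At a true Bonipar rate of 67%, the written direction gives 1.1%.

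**5. One illustrative result.** Suppose 47/76 successes on Bonipar (61.8%) and 40/76 on diclofenac (52.6%).

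- Difference: 7/76 = 9.2 points.
- Standard error: √[(0.618·0.382 + 0.526·0.474)/76] = 0.0799, so the half-width is 1.645 × 0.0799 = 13.1 points.
- Lower limit as Bonipar minus diclofenac: 9.2 − 13.1 = −3.9 points, above −10 (pass).
- Lower limit as diclofenac minus Bonipar: −9.2 − 13.1 = −22.4 points from unrounded values, below −10 (fail).

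**The case against.** The strongest reply is that this is a subscript swap and nobody would be misled. The objective is Bonipar's efficacy compared with diclofenac. Both scenarios fix diclofenac at 52% and let Bonipar vary, with a −10% margin, and the table holds P2 at 0.52 and moves P1. A lower limit that must exceed a negative margin, for a success rate with Bonipar as the test product, naturally reads as Bonipar minus diclofenac. The reversed lines sit under the power calculation, the decision rule itself contains no wrong sign, and no design figure changes. On this view the reversed probabilities describe an analyst who ignores everything except three lines.

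Much of that stands. The direction is recoverable, the design figures are sound, and the decision rule is unspecific rather than wrong, so naming the order there is a clarification. It does not remove the point. Those three lines are the formal hypotheses of the primary test, they contradict the line below them and the table, and no other section corrects them or states the order of subtraction in words.

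**Conclusion.** The concern holds. D0, H0 and H1 are written as diclofenac minus Bonipar, while the D1 line, the scenarios and the table require Bonipar minus diclofenac. It should be fixed, because following the written hypotheses would reverse the primary conclusion. At 76 per arm the chance of declaring non-inferiority at a true Bonipar rate of 62% would fall from 80.0% to 4.9%; at 42% it would rise from 5.0% to 79.8%.

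These figures assume a 52% diclofenac success rate, a 90% Wald interval and a margin of −10 points. They show the effect of a literal reading and are not the trial's expected operating characteristics. The 76 and 49 per arm, the power, the margin and the alpha reproduce for the intended direction and need no change.

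**What to change.** In the Power Calculation section, replace the three lines with:

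- D0 = −0.10 (non-inferiority margin for P1 − P2, Bonipar minus diclofenac)
- H0: P1 − P2 ≤ −0.10
- H1: P1 − P2 = D1 > −0.10

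Keep the D1 line, the P1 and P2 labels, the scenarios and the table.

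In the decision rule, specify that the difference in success rate is Bonipar minus diclofenac and that the lower limit must lie above −10 percentage points.

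Make both changes, dated, before unblinding. The cost is three lines and a few words, with no new patients or data and no change to the sample size.

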The following baseline assessments will be completed prior to administration of study drug:

- Review of medical history
- Although the risk of serious side effects is low when diclofenac is applied to the skin, pregnant women will be excluded from this study. Urine pregnancy screening will be conducted for all female subjects of childbearing potential.* Women who have a positive pregnancy test would be excluded.
- Limited skin examination and blood pressure measurement. We will exclude patients with SBP > 160 and DBP > 95 at screening.
- Collect pain information such as onset, pain intensity 24 hours prior and immediately before study drug application

*Female subjects are considered "of child-bearing potential" if they (a) are anatomically and physiologically capable of becoming pregnant and (b) they will be, or could possibly be, engaging in sexual activity with males while study interventions that pose the possibility of harm to a fetus are occurring. Note that this time period also includes any time after study activities have ended where the protocol specifies the use of contraception.

Dose, Delivery and Dispensing

After obtaining consent, subjects will be randomized to one of two study groups (Bonipar or diclofenac topical solution 1.5%), utilizing a predetermined randomization schedule in a 1:1 ratio.

The study drug, Bonipar, is stored in an opaque plastic bottle so that the contents may be protected from both direct and indirect sunlight because it is likely that sunlight could result in the degradation and/or decomposition of some of the essential oils contained in Bonipar. For blinding purposes, Diclofenac topical solution 1.5% will be stored in the same opaque plastic bottle. The bottles will be labeled either "Drug A" or Drug B" according to their designation, lot #, BUD (beyond use dating), dosing instructions, and FDA statement "Caution: New Drug—Limited by Federal law to investigational use". Thus, the drugs would be blinded to both the patients and to the investigators. Only the unblinded Clinical Research Coordinator (CRC) will have access to the randomization scheme and will have the knowledge of the dispensed drugs. To avoid any bias, the principal investigator would strongly advise the study technicians not to communicate any information regarding the 2 drugs to their investigator colleagues.

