- Include a thorough description of how risks and discomforts will be minimized (per 45 CFR 46.111(a) (1 and 2)). Consider physical, psychological, legal, economic and social risks as applicable. If vulnerable populations are to be included (such as children, pregnant women, prisoners or cognitively impaired adults), what special precautions will be used to minimize risks to these subjects? Also identify what available alternatives the person has if he/she chooses not to participate in the study. Describe the possible benefits to the subject. What is the importance of the knowledge expected to result from the research?

Herbal products have been used relatively safe for years with very few adverse effects. FIDAPIN, a topical analgesic with similar essential oil components as Bonipar (except for one herbal oil), had been studied in a randomized double-blind placebo controlled trial in 196 subjects with chronic musculoskeletal pain involving Fidapin (n=64), Diclofenac ointment (n=67) and a placebo (Jasmine oil, n=65). All groups showed a significant decrease in pain after 2 and 4 weeks. Both the diclofenac (4 subjects) and placebo group (2 subjects) developed adverse events (superficial rashes) while those receiving Fidapin did not experience any adverse effects or complications. The superficial rashes receded after discontinuation of the therapy. One subject on the diclofenac group had a progressive radicular pain and paresthesia – that subsided when it was discontinued after 8 days of use. Another observation was that Fidapin had a relatively rapid onset of action.

Since Bonipar is a topical analgesic made from naturally-occurring essential oils, the risk of developing any systemic adverse effects is highly unlikely. There is a small possibility that some patients may develop

cutaneous reactions, e.g. rashes, skin irritation etc. If such reactions were to occur, the study would be immediately halted for that subject and treatment would be offered at no costs to the patient. All subjects will have a skin examination on the treated area at baseline (before treatment). The area will be examined for the presence of the following: skin discolorations, hyperemia, skin elevations, scratch marks, wheals, pruritus, bruises, hair pattern, skin effusions and presence of any abnormal skin characteristics. AEs, if any, will be recorded at the follow-up study visit and the patient may be asked to return if the PI deems it necessary.

Costs to the Subject

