- Summarize safety concerns, and describe the methods to monitor research subjects and their data to ensure their safety, including who will monitor the data, and the frequency of such monitoring. If a data monitoring committee will be used, describe its operation, including stopping rules and frequency of review, and if it is independent of the sponsor (per 45 CFR 46.111(a) (6)).

There is no plan for formal data and safety monitoring board. Given the small target size for enrollment, we do not feel that a formal DSMB is necessary. However, all adverse events should be immediately reported to the principal investigator, [name]. The principal investigator will report any adverse and serious adverse events to the IRB during the study. PI will review and sign off on all adverse events on a weekly basis. All adverse events will be reported to the FDA at the end of the study.

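### One FDA timing, the end of the study, covers all adverse events, with no earlier route for serious suspected reactions

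*Combined protocol and SAP*

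**What the plan says.** The Data & Safety Monitoring section sets out four steps.

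- To the principal investigator: "all adverse events should be immediately reported to the principal investigator".
- To the IRB: "The principal investigator will report any adverse and serious adverse events to the IRB during the study". No time limit is attached.
- Review: "PI will review and sign off on all adverse events on a weekly basis".
- To the FDA: "All adverse events will be reported to the FDA at the end of the study".

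On independent monitoring, the same section states "There is no plan for formal data and safety monitoring board" and gives the reason: "Given the small target size for enrollment, we do not feel that a formal DSMB is necessary".

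Four other places bear on the point.

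- **Dose, Delivery and Dispensing:** the bottles of both drugs are labelled "Caution: New Drug—Limited by Federal law to investigational use", and the investigators are blinded.
- **Risk/Benefit Assessment:** the one safety study cited is a trial of a related oil mixture that differs from Bonipar in one herbal oil. Treatment stops for a subject who has a skin reaction. Adverse events are recorded at the follow-up visit.
- **Interim Analysis:** adverse effects and dropout are to be compared between the groups at about half-way (75 to 95 patients).
- **Power Calculation:** the plan is to consent 240 subjects to obtain 152 completers.

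**The concern.** A rule that names all adverse events and gives one date for the FDA puts a life-threatening suspected reaction and a mild rash on the same schedule. The authors had the distinction in hand: the sentence on the IRB separates serious from other events and places both during the study. The FDA sentence then gives a later time and carves nothing out.

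What is at stake is subject protection. If a serious reaction suspected to be due to study drug occurs early, the protocol as written does not schedule the regulator to hear of it while further subjects are being enrolled and treated. The endpoint, the power and the non-inferiority conclusion are not affected.

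**Working it through.** There is no stated figure to reproduce. The check is a reading of the safety provisions against each other, followed by the exposure that the plan implies.

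**1. Scope.** The FDA sentence covers all events. On its plain reading that includes serious ones.

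**2. Timing.** The IRB reports are placed during the study and the FDA report at its end. The two sentences stand in one paragraph, so the contrast is in the text itself.

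**3. Other routes.** No other sentence in the documents sends an event to the FDA. That the end-of-study report is the only one is therefore an inference from the absence of another. The word itself is not used.

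**4. Status of the supplies.** The caution label marks them as investigational. It is on both bottles, so it does not single out Bonipar. Of the two products, only diclofenac is described as FDA-approved, and here it may be used off-label.

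**5. What the other safeguards add.**

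| Provision | Reaches the FDA? | What is left open |
|---|---|---|
| Immediate report to the principal investigator | No | Conflicts with recording at the follow-up visit |
| IRB report during the study | No | No time limit |
| Weekly sign-off | No | Investigator is blinded, so not by arm |
| Stopping for a subject with a skin reaction | No | Applies to that subject, not to the trial |
| Half-way comparison of adverse effects | No | No reviewer and no action named |

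**6. Immediate report against visit recording.** The follow-up visit is at one week, plus or minus one day. If events are captured only there, one on the first day could wait up to 7 + 1 = 8 days. The items listed for the home diary are drug application, pain scores and oral pain medication; adverse events are not among them.

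**7. Exposure.** With 240 consented, at most 240 − 1 = 239 further subjects could pass through after an event in the first. Under 1:1 allocation, about 240 / 2 = 120 of the 240 would receive Bonipar. These are ceilings, because they count consents; the completer target is 152. No accrual period is given, so the delay in calendar time cannot be computed.

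**8. How likely is it that the rule would be tested?** The documents give no rate of serious events, so any rate r is an assumption. The chance of at least one serious event of any cause among n subjects is 1 − (1 − r)^n. With n = 240:

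- r = 0.1%: 1 − 0.999^240 = 21%
- r = 0.5%: 1 − 0.995^240 = 70%
- r = 1%: 1 − 0.99^240 = 91%

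The expected numbers are 240 × r = 0.24, 1.2 and 2.4. Events that are also unexpected and suspected to be related to study drug would be a subset of these.

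**The case against.** The strongest reply is that the trial is not unwatched. The principal investigator hears of every event at once, the IRB receives adverse and serious adverse events while the trial runs, and a between-group comparison of adverse effects is planned half-way. Treatment is topical and lasts one week. A reader might infer from the absence of a monitoring board that no independent body sees safety information; the IRB provision rules that out. What stands is narrower: there is no board or other named independent monitor of accumulating data, and none of these safeguards informs the FDA.

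Second, the documents cite no FDA reporting rule, time limit or application number. The sentence could be meant as a closing submission of all events, silent on any separate duty for serious ones. That is fair as to intent, and a reader should not infer a demonstrated regulatory breach. But the text does state a rule for all events, and staff who follow it literally would hold serious ones.

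Third, the study may mean each subject's own week, since the protocol gives the duration of the study as one week from first application. Against this, the Interim Analysis section measures half of the study in patients, and the contrast with the IRB sentence fits the whole trial better. If the subject's own week was meant, the sentence still needs rewording.

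Fourth, a reader might turn the absence of adverse effects among the 64 subjects on the related product into an upper limit for serious reactions to Bonipar. The documents do not support that. The count covers any adverse effect, the events in the other arms were mainly superficial rashes, and the product differs by one oil.

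Finally, a reader might infer that judging seriousness waits for the weekly sign-off. The protocol does not say so: it requires immediate reporting and adds the sign-off as review.

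**Conclusion.** The point holds in this form: the protocol sets one FDA timing, the end of the study, for every adverse event, and provides no earlier route for serious suspected reactions, in a trial with investigational labelling and no monitoring board. Taken literally, FDA notice of such a reaction in an early subject could wait until as many as 240 consented subjects had been through the trial.

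This rests on three readings: that all means all, that the end of the study means the end of the trial, and that no separate FDA reporting plan exists outside these documents. The size is a ceiling, because not every consented subject need be treated and because the principal investigator or the IRB could act sooner on what they receive. No rate of serious reactions to Bonipar can be drawn from the documents.

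**What to change.** Replace the FDA sentence with a two-tier rule, for example:

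> Serious, unexpected adverse events suspected to be related to study drug will be reported to the FDA while the trial is in progress, at the same time as the report to the IRB and within the time limits that apply to the investigational application. All other adverse events will be summarised to the FDA when the trial ends.

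The sponsor should fill in the applicable limits, since the documents do not give them.

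In the same amendment, reconcile immediate reporting in the Data & Safety Monitoring section with recording at the follow-up visit in the Risk/Benefit Assessment, so that it is clear how an event between visits reaches the principal investigator. It would also help to name who reads the half-way comparison of adverse effects.

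The cost is a wording amendment and a few reports at most. No new staff, visits or procedures are needed.
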